### **Study Design.**

*Measures and Measurement Plan.* All measures chosen for use in the study are in the public domain and have strong psychometric properties (e.g., internal consistency, test-retest reliability, concurrent validity). There will be two streams of data collection involving students. The first will be data collected to reflect school-wide impacts of the Partnership Condition focusing on academic record variables of students' grades, attendance, lateness and discipline referrals (including office discipline referrals and suspensions), and school climate. School-wide academic record data will be collected for all students and de-identified to the research team (it is considerably less burdensome for schools to share deidentified data for all students than to share for a sample of them). School climate data will be collected for a sample of about 60 students (3 randomly selected classrooms), and 25-40 staff (requesting all staff complete) at each of the 22 schools. School-wide academic record data will be collected once annually for the academic year prior to study start (2018-19), and will be collected each year for the three years of intervention vs. comparison, per procedures that we are replicating based on the current NIJ-funded RCT. Selected students and staff will complete the School Climate Survey (SCS) a free, online school climate survey from the US Department of Education (<https://safesupportivelearning.ed.gov/edscls>). The SCS is available as a web-based platform and includes a suite of school climate surveys for students, instructional staff, and non-instructional staff. Staff and students will be asked to

PRINCIPAL INVESTIGATOR: [name]

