*Aim 2: Evaluate the impact of the Partnership enhancements on students' social, emotional/behavioral (EB), and academic outcomes.* For this primary aim, there will be two sub-aims: Aim 2a will evaluate the impact of the Partnership enhancements on school-wide academic record variables of grades, attendance, lateness and discipline referrals. Aim 2b will focus on students receiving Tier 3 services and will assess their social and emotional/behavioral (EB) functioning. To assess social functioning, the Child and Adolescent Social and Adaptive Functioning Scale (51) will be completed by students. The CASAFS includes 24 items measuring students' functioning in four key social roles: school performance, peer relations, family relations, and home duties/self-care. Additionally, both "internalizing" EB problems, which include problems of depression, anxiety and exposure to trauma, and "externalizing" EB problems, which include conduct and attention problems, will be measured for students receiving Tier 3 services. Student EB functioning will be measured by parent and student report forms of the Brief Problem Checklist (52), a 12-item questionnaire that measures externalizing and internalizing problems. Derived from the comprehensive Child Behavior Checklist (53), it is designed for repeated periodic assessment of clinical progress, yielding both an internalizing and externalizing subscale (52). Please note that academic variables collected above school-wide for stream 1 data collection, will also be used for stream 2 data collection for students receiving Tier 3 services. Changes in the above variables will be assessed for students for the academic quarter before receiving mental health services and the academic quarter after services have been completed.

*Additional Measures.* In addition to measures directly reflecting study aims, secondary aims will be addressed by measures reflecting the potential impact of the two Partnership enhancements will be collected at the same time intervals for students receiving Tier 3 services. For the enhancement focused on mental health education and stigma reduction, students will complete The Guide Curriculum Assessment (GCA) reviewed previously (43,44). The GCA includes subscales assessing Mental Health Literacy in three dimensions: Mental Health Knowledge (MHK; 28 items),

PRINCIPAL INVESTIGATOR: [name]

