**Analytic Plan.** The proposed project is a cluster-randomized controlled trial (J=22 schools; 11 per treatment arm) comparing the efficacy of Wellness vs. Partnership services. As a general analytic plan, we will use hierarchical linear modeling (HLM) to evaluate the project aims. Specifically, we will use two-level HLM models to account for students being nested within schools. Though one might conceptualize this proposal as a three-level model (i.e., students nested within schools, and schools nested within sites), it would be neither feasible nor recommended to model site as a multilevel variable given there are only two sites in the design (56). In line with best practice, we will integrate site (i.e., SC vs. MD) as a covariate in the statistical models to contain any potential effects of this variable. Based on prior research conducted by the team, we expect intraclass correlations (ICCs) to warrant the incorporation of random intercepts to account for violations of independence. We will also test independence assumptions for the treatment parameters to determine how sensitive treatment effects are to potential violations of independence, and will include random slopes to account for nested treatment effects if ICCs exceed .01. For transparency, we will report both fixed and random effects (i.e. intercepts and slopes) of the model. Additionally, we will iteratively subset the model using a k-1 sensitivity analysis to determine the influence of individual sites on parameter estimates. We will estimate statistical models using full information maximum likelihood to accommodate any missing data (57). We will use maximum likelihood with robust standard errors to estimate models that include the Zero Inflated Poisson link function for count

PRINCIPAL INVESTIGATOR: [name]

outcomes (e.g. absences, referrals). This general analytic framework will be used in aims 1 and 2. Details, exceptions, and modifications to it are discussed below.

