Given the experiment will examine intent-to-treat effects in a real-world setting, we will conduct analyses to investigate variability in implementation and compliance to enhance causal effect interpretation of clients "as treated." Specifically, we will use a Bayesian Additive Regression Tree approach (BART; 61) to delineate the impact of key treatment assumptions (e.g., compliance, fidelity, etc.), as well as to estimate the impact of assumption violations on the estimation of causal effects in the design. BART is an extension of Classification and Regression Tree (CART) models that is based on a recursive partitioning algorithm that explains variation in the outcome through repeated splits of the data into homogenous subgroups that are similar on predictor variables. One significant strength of BART is that it is capable of handling a large number of predictors and incorporates higher-order interactions that may be excluded from parametric analysis. Research indicates that BART is insensitive to tuning parameters and produces more accurate estimates of treatment effects compared to other methods of analyzing treatment effect heterogeneity (i.e., propensity score matching, propensity-weighted estimators, instrumental variable procedures, and regression adjustment; 61). Note that this BART enhancement to the randomized, experimental design should not be mistaken for a Bayesian trial design.

*Power considerations.* The design originally included a planned sample size of approximately N=2800 (1400 per arm) for Aims 1 and 2. We previously revised power estimates for these study aims that consider the possibility of reduced participant involvement given COVID-19 and recruitment challenges more broadly, with a revised sample size of approximately N=1400 (700 per arm). With the research study period concluding in June 2023, we have revised the enrollment projection to a conservative estimate of N=1225. With our currently active sites (J=22) and the total number of students enrolled in the study (N=1225, including expected spring 2023 enrollment), assuming 30% of variance

PRINCIPAL INVESTIGATOR: [name]

explained in the primary outcomes by pre-test covariates, and 80% power, we have a minimum detectable effect size (MDES) of .29. If we reach our goal of 1400 students, we will be at .28.

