There are essentially six classes of student participants, with groups based on grade level at the start of the intervention vs. comparison (IvC) period of the study, which begins in the 2019-20 school year. There is a four-year IvC period, 2019-20, 2020-21, 2021-22, and 2022-23. Group A will be in the 6th grade in 2019-20, with students experiencing 1-3 years of services in this time interval. These students could have received services in 6th, 7th and/or 8th grades during the IvC period. Group B will be in the 7th grade in 2019-20, with students experiencing 1-2 years of services in this time interval. These students could have received services in 7th and/or 8th grades during the IvC period. Group C will be in the 8th grade in 2019-20, with students experiencing 1 year of services in this time interval. Group D will enter the study in 6th grade in 2020-21. Group E will enter the study in 6th grade in 2021-22. Group F will enter the study in 2022-2023 while in 6th grade.

*Identifying eligible participants.* Participants already receiving treatment and those newly referred for services will be eligible to participate and recruited by their SBH clinician. Throughout the implementation phase (years 1-4) each school will use their existing referral process to identify students in need of treatment which will be followed up and confirmed by the SBH clinician prior to enrolling them in the study.

*Overcoming barriers to enrollment.* In addition to our successful experiences with the opt-out procedure to be used for stream 1 data collection, both mental health centers have participated in extensive and similar research with the investigators leading this study. The SAB will provide input on the development of consent materials, and methods of communication, making sure that they are appealing. The process of utilizing e-consent will be convenient and streamlined for Tier 3 participants. Additionally, participant incentives are proposed, in the amount of \$20 per parent assessment battery, and a token of appreciation for each student assessment battery to incentivize participation.

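### The 2018-19 school-wide records have no stated role in the Aim 2a model; they should enter as a school mean beside site, because most grade-years can have no own-student baseline

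*Combined protocol and SAP*

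**What the plan says.** **Outcome.** The Aim 2 text states: "Aim 2a will evaluate the impact of the Partnership enhancements on school-wide academic record variables of grades, attendance, lateness and discipline referrals". Aim 2 is described as primary.

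**Baseline.** The Measures and Measurement Plan states: "School-wide academic record data will be collected once annually for the academic year prior to study start (2018-19". It then says these records "will be collected each year for the three years of intervention vs. comparison". They reach the research team de-identified.

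**Period and classes.** The Recruitment Plan states: "There is a four-year IvC period, 2019-20, 2020-21, 2021-22, and 2022-23". It also states "Group A will be in the 6th grade in 2019-20", puts Group B in grade 7 and Group C in grade 8 that year, and continues "Group D will enter the study in 6th grade in 2020-21. Group E will enter the study in 6th grade in 2021-22". Group F enters grade 6 in 2022-23.

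**Model.** The Analytic Plan sets out a two-level model for Aims 1 and 2 with full information maximum likelihood (FIML) for missing data. The one covariate it names is site: "we will integrate site (i.e., SC vs. MD) as a covariate in the statistical models". Difference scores are specified only for students receiving Tier 3 services.

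**Schools.** Two of the 22 schools joined in Year 3, one per condition (Training and experience of recruitment personnel).

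**The concern.** One pre-intervention year is scheduled for the school-wide outcomes, and no text says how it enters the Aim 2a analysis. An analyst could use site only, a school mean, the student's own value, or change from that value. These choices differ in precision and, for the last two, in which students and years contribute. With 22 randomised schools, precision depends almost wholly on between-school variance, which is what a baseline school mean can reduce. Leaving the choice open risks losing that gain and allows the choice to be made after the data are seen.

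**Working it through.** **1. The plan's own figure, and why it is not the yardstick.** Power considerations gives a minimum detectable effect size (MDES) of .29 for 1,225 students in 22 schools, with 30% of variance "explained in the primary outcomes by pre-test covariates, and 80% power". ICC and alpha are not stated. Assume two-sided 5%, the 30% at both levels, df 20 (multiplier 2.946) and 1225/22 = 55.7 students per school. An ICC of .059 then gives

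2.946 × √[(4/22) × (.059 × .7 + .941 × .7/55.7)] = 2.946 × .0983 = .29.

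So .29 is attainable, but it cannot be verified without the ICC. It refers to the enrolled students, not to the school-wide population of Aim 2a.

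**2. Who can have an own 2018-19 record.** Normal grade progression is assumed.

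| Group | Grade in 2018-19 | Grade-years, four years | Grade-years, three years |
|---|---|---|---|
| A | 5 | 3 | 3 |
| B | 6 | 2 | 2 |
| C | 7 | 1 | 1 |
| D | 4 | 3 | 2 |
| E | 3 | 2 | 1 |
| F | 2 | 1 | 0 |
| Total | | 12 | 9 |

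Only B and C were in middle-school grades, which gives 2 + 1 = 3 grade-years. Without an own study-school record: 12 − 3 = 9 of 12 (75%) over four years, or 9 − 3 = 6 of 9 (67%) over three. The three covered cells are grades 7 and 8 in 2019-20 and grade 8 in 2020-21. Even there, no year-to-year linkage of the de-identified school-wide records is described.

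**3. What a school-level baseline could add.** Inputs: J = 22 schools and 80% power (Analytic Plan, Power considerations); n = 600 per school (Recruitment Plan). Assumptions: two-sided 5%, a linear outcome, the ICC, and R², the share of between-school variance explained by the 2018-19 school mean.

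MDES = (t.975 + t.80) × √[(4/J) × (ICC × (1 − R²) + (1 − ICC)/n)], with df = J − 3 for site only and J − 4 with the baseline added.

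At ICC .05 with 22 schools:

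- Site only: (2.093 + .861) × √[.1818 × (.0500 + .00158)] = 2.954 × .0968 = .286.
- R² = 30%: (2.101 + .862) × √[.1818 × (.0350 + .00158)] = 2.963 × .0816 = .242.
- R² = 0: 2.963 × .0968 = .287. The lost degree of freedom therefore costs about .001.

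| Schools, ICC | Site only | R² 10% | 30% | 50% | 70% |
|---|---|---|---|---|---|
| 22, .02 | .185 | .177 | .158 | .136 | .110 |
| 22, .05 | .286 | .273 | .242 | .206 | .163 |
| 22, .10 | .401 | .382 | .338 | .287 | .224 |
| 20, .05 | .302 | .288 | .255 | .218 | .172 |

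The 20-school row drops the two schools added in Year 3. The student term is .00158 of .05158, about 3%, so the choice of n matters little. That the site-only value at ICC .05 also rounds to .29 is a coincidence with the plan's figure.

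**The case against.** The strongest reply is that the plan proposes nothing wrong for Aim 2a; it is only silent. The Analytic Plan calls itself general, explains why site is included, and does not say that site is the only covariate. That stands: the 2018-19 year is unassigned, not discarded.

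Two stronger readings are tempting and not supported.

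- A reader might infer that the analysis would delete 9 of 12 grade-years. No text proposes adjusting Aim 2a for the student's own 2018-19 value. Difference scores are confined to Tier 3 students, whose academic change is measured from the quarter before services to the quarter after. FIML could also keep rows that lack a pre-test if the pre-test is modelled jointly, although classes without one by design would get no individual adjustment.
- A reader might infer that the 30% credit in Power considerations fails because most classes have no pre-test. That credit concerns the 1,225 enrolled students, who have intake measures and a pre-service quarter whatever their class.

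Several limits on the size also stand. The R² values are assumed, and pandemic-year outcomes may relate weakly to 2018-19. Randomisation is stratified on a composite that includes school test performance; if strata were also modelled, less between-school variance would remain to explain. Absences and referrals are to be analysed with a zero-inflated Poisson model, which a linear MDES does not describe directly. The calculation uses one mean per school, and a same-grade mean also varies within school. Finally, no text shows that 2018-19 records exist for the two added schools.

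**Conclusion.** The point holds as a gap in specification with a probable loss of precision. It is not a source of bias, since randomisation protects the comparison with or without the baseline. A pre-intervention year is scheduled for the Aim 2a outcomes and no model text uses it. The student's own value cannot be the general baseline, because 9 of 12 grade-years (four-year period) or 6 of 9 (three record years) cannot have one from a study school. Entered at school level, the baseline would lower the MDES at ICC .05 from .29 to between .27 and .16 for R² of 10% to 70%. The proportional gain is similar at ICC .02 and .10. These figures rest on assumed ICC, alpha and R², a linear outcome, and 2018-19 records for all 22 schools. If R² is near zero, the gain vanishes and the cost is negligible.

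**What to change.** In the primary Aim 2a model, add the school's 2018-19 mean of the same outcome as a covariate beside site, for all six classes and all record years. Use either the same-grade mean with grade terms or the overall school mean, and state which before analysis. Any analysis using the student's own 2018-19 value should be secondary, restricted to Groups B and C, and conditional on records that can be linked.

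Obtain 2018-19 records for the two schools added in Year 3, or state how those schools are handled, for example with a sensitivity analysis in the 20 original schools. Reconcile the three record years in the measurement plan with the four-year period in the Recruitment Plan. Power considerations needs no change on this account.

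The cost is a few sentences in the analysis plan, about one between-school degree of freedom, and a records request for two schools if their 2018-19 data are not in hand.

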**Site Selection.** Proposed study sites were selected based on factors related to feasibility as well as their potential for providing a representative patient sample. Both the [REDACTED] Mental Health Center ([REDACTED] MHC) and the CSMH, have long histories of collaboration with investigators of this study. This existing relationship provides many benefits in avoiding common barriers to implementation. The two sites offer complementary demographics with CSMH serving youth who are primarily urban and African American, while [REDACTED] MHC serves a suburban and rural youth population that is more diverse racially and ethnically, and both sites serve low and middle income families, allowing us to evaluate for a variety of outcomes in subgroup populations. Additionally, incorporating the two interventions into routine SBH practices will facilitate findings that are immediately applicable to real world contexts.

PRINCIPAL INVESTIGATOR: [name]

## DISSEMINATION AND IMPLEMENTATION POTENTIAL

---

A. Building on the platform of the ECHO program (25, 26) and guidance by the Stakeholder Advisory Board (SAB), dissemination of study findings will begin in Year 5, with comparison schools joining ongoing ECHO clinics held for intervention schools (in Years 1-4). In Year 5, parent leaders and the study team will conduct presentations to each of the 22 schools, the sponsoring school districts, and the two mental health centers, reviewing study findings and making them accessible through the study website. Signs about the study and its findings will be posted throughout the centers so that patients and families receiving treatment within them can learn about the study. In addition, study notifications and consent/assent forms for families will mention the study website and availability of findings as of Spring 2023, and our hope is that study participants access these resources to learn about study findings and lessons learned. In addition, we will make available as a public domain resource and broadly disseminate the study implementation manual, increasing the ability of other sites to implement the six-component Partnership intervention. Further, in Year 5, the ECHO platform will be used for sharing of findings and dialogue with professional organizations (e.g., National Association of School Psychologists, National Council for Behavioral Health), and state, local and federal policy leaders. Our connections to state and national groups with a vested interest in school behavioral health (SBH) will be facilitated by networks the PI and Co-I/MD site-PI lead, in particular, the Southeastern School Behavioral Health Community (SSBHC, see [www.schoolbehavioralhealth.org](http://www.schoolbehavioralhealth.org)) and the Center for School Mental Health (CSMH, see <http://csmh.umaryland.edu>), with an anticipated reach to more than 100,000 stakeholders by study end. More than 26,000 schools in the nation are implementing MTSS, as in systems such as Positive Behavioral Interventions and Supports (PBIS, see [www.pbis.org](http://www.pbis.org)). Within these efforts, there is increasing priority on effective SBH (17). The CSMH reports a dramatic increase in technical assistance requests for evidence-based mental health practice implementation in schools, with a marked uptick following incidents of mass violence in schools. With certainty, national centers for SBH and PBIS will use findings from the proposed study in their ongoing work to expand and improve the quality of SBH and MTSS in the U.S., and these centers have close working relationships with the professional organizations and networks mentioned, and many others.

PRINCIPAL INVESTIGATOR: [name]

Please also note that the PI, Co-I/MD site-PI and research team have significant publication records in the SBH area, with publications reflecting breadth in outlets of peer-reviewed empirical articles and reviews, books and book chapters, monographs, widely disseminated white papers, e-books, research briefs, newsletters and others. As an example, for the recently completed PCORI Engagement Award, the PI and SAB co-chair led a series of 4 issues (the entire 2017 volume) of the Report on Emotional & Behavioral Disorders in Youth, including 15 articles focused on ways to increase the effectiveness of stakeholder driven SBH (75-78). With significant input from the SAB, user-friendly briefs on study findings and lessons learned will be developed and improved after each year, and finalized and broadly disseminated in Years 4 and 5 of the study via the SSBHC and CSMH networks and others the study team is connected to (see [www.carolinanetwork.org](http://www.carolinanetwork.org), [www.pbis.org](http://www.pbis.org) , [www.smhile.com](http://www.smhile.com)).

B. Three prominent barriers to disseminating and implementing results from this study in other settings are federalism, information management challenges, and discipline and youth-serving system silos. Federalism. A major issue affecting the scaling up of evidence-based strategies to improve student functioning is federalism, including the emphasis on states' rights and local control, which can result in highly variable experiences across communities and states, and even within them (79). To address this challenge, in our work we have emphasized a community of practice approach (80), and effectively convening groups at local and state levels to support the increasing coherence and impact of SBH initiatives, as in the work occurring through the SSBHC and CSMH. In particular, states play a crucial role in overcoming the challenge of federalism, when they assume liaison roles between federal and national initiatives and support, and experiences and resources from other states, and getting information and resources down to counties/school districts, and in turn tracking and disseminating information on best practices occurring at local levels. Overcoming challenges of federalism has been a major focus of the CSMH; PI, [name], and Co-I and Maryland Site PI, [name]. Both the CSMH and the SSBHC offer opportunities for state leaders to present and share innovative initiatives during national and regional conferences and webinars, with explicit support for promoting cross-state innovation adoption. We are confident that these methods will help to overcome the challenge of federalism, and provide an important national exemplar on accomplishing the same. Information Management. Rapidly managing diverse sources of information through diverse media is an increasing challenge (81). We will help diverse stakeholders use information from the study by developing materials in multiple and user-friendly formats as in the above broad array of strategies planned for dissemination, repetitiveness in sharing key messages, and identifying and publicizing the experiences of exemplar sites, and their experiences in moving toward greater effectiveness and impact. Two specific strategies that have been employed by our team are Playbooks and Infographics. To date, the CSMH has published two Playbooks that succinctly review best practices and tips from the field on critical practice strategies. The two published playbooks (School Mental Health Screening, School Mental Health Teaming) shared lessons from the field on how to implement tested strategies for practice improvement, with easily understandable text and language and ready-to-use tools. For example, the Teaming playbook includes action steps for schools and communities to engage in community-partnered SBH models, with templates for memoranda of understanding between schools and communities and tools to define roles and responsibilities of school- and community-employed support staff. Infographics have also been used by the CSMH as a tool for communicating the need for and value of providing mental health services in schools. These types of communication tools will be used to communicate findings from the proposed study in a manner that is easily digestible and usable by others in the field. Discipline and Youth-Serving System Silos. An unfortunate reality is that discipline and youth-serving systems often operate in isolation (16). Since the SBH field is inherently interdisciplinary, and operates in the nexus of many systems, efforts may be impeded when disciplines and systems fail to interact meaningfully. As above, to address this challenge, we will connect to the SSBHC, CSMH and other communities of practice, and develop a range of interactive information sharing strategies, distilling information down into user-friendly briefs and infographics, and using a range of approaches (ECHO video conferencing, professional presentations, smaller meetings and discussion forums) to move discussions to dialogue, collaboration, and positive policy change as guided by the SAB and PCORI project officers. We look forward to discussions with and active guidance from PCORI project officers on building strategies for meaningful interdisciplinary and cross-system collaboration to advance effective SBH initiatives

PRINCIPAL INVESTIGATOR: [name]

and to share lessons learned and findings from exemplary initiatives as in the intervention tested in the proposed study.

PRINCIPAL INVESTIGATOR: [name]

